Hospitalization for angina (or non-MI acute coronary syndrome) is defined as overnight hospitalization for symptoms, such as chest pain, chest tightness, or shortness of breath, produced by myocardial ischemia that do not result in myocardial infarction, but are treated medically or surgically during an overnight stay. The symptoms generally last less than 20 minutes, and may have occurred prior to the admission. This definition also includes hospitalizations for the diagnosis of angina/symptomatic coronary artery disease from a physician based on history and a positive diagnostic test (angiography, exercise stress testing, perfusion scan or stress echocardiogram).

Coronary/carotid revascularization: Revascularization is confirmed when participants undergo urgent or elective coronary bypass grafting, angioplasty, endarterectomy, thrombectomy, or any similar procedure intended primarily to ameliorate coronary/carotid artery stenoses.

Death attributable to cardiovascular disease (CVD): death attributable to CVD events, defined as those that comprise the MACH15 primary outcome (specifically MI, ischemic stroke, hospitalized angina, and coronary/carotid revascularization), and based on temporal relationship considering event medical records (e.g., hospitalization for MI or stroke), or postmortem findings related to an acute CVD event.

Other: In addition to the above, MACH15 will assess additional diabetes related outcomes:

- Progression among normoglycemic and pre-diabetes individuals to ADA-defined diabetes;
- Progression among normoglycemic individuals to ADA-defined prediabetes.

Both these ADA-defined outcomes will be confirmed by two measurements of either HbA1c or fasting plasma glucose obtained at the annual clinic visits or based on documented use of medication treated diabetes starting between in-person clinic visits.

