Other questionnaires									
Smoking History			X						
Fagerstrom Test of Nicotine Dependence			X				X		X
EQ-5D-5L			X				X		X
PHQ-9	X						X		X
Food Frequency Questionnaire			X ⁹				X ⁹		X ⁹
Physical Activity Measure			X ⁹				X ⁹		X ⁹
Verify eligibility			X						
Health Coaching									
Counseling on run-in (optional)/washout	X	X							
Behavioral and health counseling for intervention and adherence		X	X	X	X	X	X	X	

Abbreviations: mos = months; Q = every; CVD = cardiovascular disease; AST = aspartate aminotransferase; ALT = alanine transaminase; GGT = gamma-glutamyl transferase; HDL = high density lipoprotein; LDL = low density lipoprotein; AUDIT = Alcohol Use Disorders Identification Test; Y-BOCS-hd = Yale-Brown Obsessive Compulsive Scale-heavy drinking; PHQ-9 = Patient Health Questionnaire-9.

¹ Randomization and counseling for adherence may be done on same or different visit from Baseline Visit per site preference.

² Quarterly phone calls except when quarterly calls coincide with an annual in-person visit.

³ Separate informed consents may be obtained for collection and storage of samples to be used for genomic analyses and to collect alternate contact information where required by local regulations.

⁴ Optional annual collection per participant consent and/or clinical site ancillary studies.

⁵ If the participant has had these labs within 24 months, historical values may be used.

⁶ A self-report physician diagnosis of diabetes would be enough for screening and for determining the cardiovascular risk score (lab value is not required). However, if the participant does not know, either fasting glucose or HbA1c (non-fasting) should be used (historical values within 24 months may be used).

⁷ To assess for incident diabetes, all participants must have fasting glucose or HbA1c per clinic preference (fasting not required for HbA1c) drawn at the baseline visit and annually thereafter. If the value is above the ADA-defined cutoff for pre-diabetes, the participant will be asked to return to the clinic for a second blood draw to confirm the diagnosis. (Participants with known diabetes or that have been started on diabetes medication during the trial do not need to have a second blood draw.)

⁸ Does not need to be repeated if drawn at screening. If historical values were used to calculate AHA Risk Score, a baseline Total Cholesterol must be obtained.

⁹ Optional on-line questionnaires.

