6.1.1.4 CLINICAL MEASURES

Seated blood pressure and pulse will be assessed in a standardized manner, after a 5-minute rest period using a standard automated device or, if necessary, a manual device. The preferred method is the automated device as it offers reduced potential for biases and decreased demand on staff in terms of training and effort in data collection. Three measures will be taken 1 minute apart and the average of the 3 measures will be obtained. Blood pressure and pulse will be collected at the screening visit, baseline visit, 3 month visit, 6 month visit, and all annual visits.

Concomitant medications are required to be recorded at screening, baseline and then reviewed and revised at annual follow-up visits. Prescription and non-prescription medication use will be collected and generic names will be recorded and entered in the database. Clinical sites may choose to collect information about medications more frequently. Participants will be asked to bring all medications to the screening, baseline, and annual visits. However, other appropriate sources for obtaining this information may also include current pharmacy action profiles, and/or verification of medications documented in the medical record.

Medical history is collected at screening to determine eligibility (see *Chapter 4: Participant Enrollment*). Data regarding presence of comorbidities are important for descriptive purposes, subgroup analyses and prognostic analyses. Clinical sites may supplement participant self-report with medical record information, if available.

Serious adverse events (SAEs) and selected adverse events (AEs), further referred to as MACH15 AEs, will be ascertained and reported during all participant visits (phone and in-person) beginning at the 2 week phone call. In addition, once participants have provided consent, any SAEs/MACH15 AEs that are

spontaneously reported by the participant or proxy at any time, or that are discovered in other ways are to be documented. Adverse event ascertainment and classification is described more fully in *Chapter 7: Assessment of Participant Safety*. Briefly, medical events and symptoms will be solicited at each visit, using a standard form that is administered by clinical site staff that may be unmasked to the intervention arm assignment. SAEs and MACH15 AEs will be reviewed at the clinical site by a masked clinician who will make the assessment as to relatedness.

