6.3.6 FOLLOW-UP

After the baseline/randomization visit, participants will be seen in clinic for subsequent visits at 3 months, 6 months, 12 months, and then annually until close-out. Follow-up phone calls will occur at 2 weeks, 4 weeks, and 9 months during the first year, and every 3 months thereafter (except for annual

visits when participants are seen in clinic). See Table 6.1: Measures and Frequency for the sequence of events and special considerations (e.g., fasting visits) and the MOP regarding visit windows.

6.3.6.1 3 AND 6 MONTH IN-PERSON VISITS

- Contact information updated
- Blood pressure and pulse
- Blood draw for AST, ALT, GGT, HDL-C
- Timeline Followback (7-day)
- YBOCS-hd (3 items)
- Health Coaching (for adherence)
- Assessment for SAEs and MACH15 AEs
- Assessment for CVD outcomes

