8.1.1 PRIMARY AND SECONDARY OUTCOME ANALYSES

The primary analysis will assess the significance of any difference observed in the distribution of time from randomization until occurrence of the primary endpoint, an expanded cardiovascular disease (CVD) endpoint which includes death from any cause, using censored survival data analysis methods for clustered data. A detailed definition of the endpoint is given in *Chapter 3: Trial Design and Clinical Outcome Measures*. Kaplan-Meier estimates of survival will be obtained for participants randomized to each arm, taking into account household clustering,¹ and the log-rank test for clustered data,²⁻⁵ stratified by clinical site, and will be used to assess the statistical significance of any differences observed. The primary comparisons of intervention groups will be performed according to the “intention to treat” principle: all randomized participants will be grouped according to their intervention assigned at randomization. Hazard ratios and 95% confidence intervals will be calculated using Cox regression model for clustered data,^{6,7} adjusted for clinical site by a set of indicator variables. Estimates for the proportion of participants who remain event-free at pre-specified time points, and the associated confidence intervals, will be calculated similarly. Log-log plots of survival will be used to examine the assumption of proportional hazards, and effect modification by time since randomization will be assessed through the introduction of indicator variables for each 6-monthly or annual time period. If the proportional hazards assumption is not justified, in secondary analysis, we will report time-specific effect estimates and consider the use of accelerated failure time models which may provide a more parsimonious fit to the data. Should best practices for statistical analysis of trials with designs similar to MACH15 develop during the course this trial, the analysis plan will be revised accordingly. The analysis of the secondary endpoint, incidence of diabetes, will be conducted as described above.

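### For incident diabetes, the proportional-hazards check and the 6-monthly or annual period effects cut time where the annual blood draws fall, so small arm differences in visit timing can mimic a changing effect

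*Combined protocol and SAP*

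**What the plan says.** Section 8.1.1 sets out a clustered log-rank test, a Cox model, log-log plots and a check for a changing effect: "effect modification by time since randomization will be assessed through the introduction of indicator variables for each 6-monthly or annual time period". If proportional hazards fails, "in secondary analysis, we will report time-specific effect estimates", and accelerated failure time models are considered. For diabetes the section adds only: "The analysis of the secondary endpoint, incidence of diabetes, will be conducted as described above".

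The measurement schedule for diabetes differs from that for cardiovascular events:

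- Table 6.1, footnote 7, has glucose or HbA1c "drawn at the baseline visit and annually thereafter". The table also shows a close-out draw.
- At 3 and 6 months, section 6.3.6.1 lists "Blood draw for AST, ALT, GGT, HDL-C", with no glycaemic test.
- Section 3.5.2 defines the event by two laboratory values "obtained at the annual clinic visits or based on documented use of medication treated diabetes starting between in-person clinic visits".
- Section 6.1.1.4 states: "Concomitant medications are required to be recorded at screening, baseline and then reviewed and revised at annual follow-up visits". Sites may collect medications more often.
- The quarterly outcome form described in 6.1.1.4 and Table 6.1 covers cardiovascular outcomes.

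No section says whether a lab-detected case is dated to the first abnormal draw or to the confirmatory one, and no grouped-time or interval-censored method is named.

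**The concern.** Cardiovascular events have their own dates, so continuous time suits them. A lab-detected diabetes case is known only to have arisen between two annual draws, and its recorded date is in effect a visit date. Two consequences follow for the time-specific analysis.

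First, no lab-detected case can fall in months 0-6, so a half-year hazard ratio there rests on medication starts alone.

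Second, the nominal visits sit on the cut-points. A case found at the 12-month visit counts in one period if the visit is slightly early and in the next if it is slightly late. If the arms differ in punctuality, cases move across the cut in different proportions and the period ratios move with them.

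At stake is a reported change over time in the effect of alcohol on diabetes that comes from the visit calendar, because 8.1.1 commits to time-specific estimates when proportional hazards looks wrong.

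**Working it through.** **Inputs from the documents.** Diabetes-free sample 5,850, so 2,925 per arm; abstention-arm rate 0.017 per person-year; relative risk 0.75; 10% non-adherence; 1% annual loss; two-sided 0.05 (section 8.2). Follow-up 4.5-7.5 years, mean 6 (section 11.4).

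**Assumptions not in the documents.** Visit-date SD of 30 days or 0.7 month; alcohol-arm visits later by 7 or 14 days (or 0.25 or 0.5 month); share of cases dated by medication start 0%, 20% or 30%.

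**1. Reproduce the plan's figure.** The dilution in 8.2 is 0.9 × 0.82 + 0.1 = 0.838. The same rule for diabetes gives 0.9 × 0.75 + 0.1 = 0.775. Exponential event times and losses with uniform 4.5-7.5 years give about 275 + 216 = 491 events. Schoenfeld power = Φ(√(491/4) × |ln 0.775| − 1.96) = 80.6%, against 80% in Table 8.2.

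**2. First half-year.** If onset were seen at once, months 0-6 would hold about 2,925 × 0.017 × 0.5 = 25 abstention and 25 × 0.775 = 19 alcohol cases. With lab detection they hold none. If 20% of cases are dated by medication start, simulation puts about 5 and 4 there. The standard error of the log ratio is then √(1/5 + 1/4) = 0.67, so the 95% interval spans a factor of exp(1.96 × 0.67) = 3.7 either way.

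**3. Equal timing.** With a true ratio of 0.775 and no arm difference, simulated half-year ratios with events are 0.75-0.79. There is no bias.

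**4. Unequal timing, by hand.** Let visits be centred on the cut in one arm and shifted by d in the other, with SD s. The share found before the cut is 0.5 and Φ(−d/s) respectively. The period ratios are then approximately:

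- before the cut: HR × Φ(−d/s) / 0.5
- after the cut: HR × [1 − Φ(−d/s)] / 0.5

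| HR | s | d | Φ(−d/s) | before | after |
|---|---|---|---|---|---|
| 1 | 30 days | 7 days | 0.408 | 0.82 | 1.18 |
| 1 | 30 days | 14 days | 0.320 | 0.64 | 1.36 |
| 0.775 | 0.7 month | 0.25 month | 0.361 | 0.56 | 0.99 |
| 0.775 | 0.7 month | 0.5 month | 0.238 | 0.37 | 1.18 |

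Simulation agrees. At HR 1 and SD 30 days, the earlier half-years alternate at about 0.8/1.2 (7 days) and 0.63/1.35 (14 days). At HR 0.775, months 6-12 and 12-18 read 0.56 and 1.01 (0.25 month), or 0.38 and 1.20 (0.5 month). The swing narrows late in follow-up as close-out draws spread the dates.

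**5. The annual option.** With cuts at 12, 24, ... months, year 1 receives only the early part of the first visit round. It reads about 0.83 (7 days) and 0.63 (14 days) at HR 1, SD 30 days. Years 2-5 are nearly right, because each gains late cases from one visit round and loses them from the next.

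**6. Would it be noticed at trial size?** At n = 5,850, HR 1, SD 30 days and lab detection only, a 5% test of heterogeneity over half-years rejects in 5%, 20% and 77% of trials at shifts of 0, 7 and 14 days. With annual cuts it rejects in 4%, 7% and 17%. Across settings with SD 21 or 30 days and 0% or 30% medication starts, visit-aligned annual periods reject in 4-7%, with ratios of about 1.0.

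**7. What does not move.** With lab detection only and a true ratio of 0.775, the overall ratio stays at 0.77-0.78 with 487-489 events in every timing scenario. Grouping by scheduled visit returns 0.76-0.81 for visits 1-7.

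**The case against.** The strongest reply is that the harm needs an arm difference in timing that no document reports. Section 6.1.1.4 plans outcome assessment in the same way and on the same schedule in both groups. Section 9.2.3 describes target dates and window alerts for every participant, and section 5.1 says intervention intensity is similar in both arms. The plan also leaves the period length open, so half-years are not fixed, and annual cuts remove much of the false-positive risk. All of this stands, and it limits the point to fragility under conditions that cannot be checked here.

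It does not dispose of the point. Participants know their arm. Section 5.2 ties alcohol supply or reimbursement to adherence and responsiveness but leaves anything for the abstention arm to site discretion, and section 5.4.2 tailors contact to the arm. A difference of one or two weeks is therefore plausible, though not shown. The annual option still misplaces year 1, and the first half-year is empty of lab cases whatever the timing.

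Two stronger readings should be resisted. A reader might infer that diabetes is sought only at annual visits. Section 3.5.2 adds the medication route, which can place an event in any half-year, and section 6.3.7 allows close-out assessments at early termination. A reader might also infer that half-year ratios always measure punctuality. With equal timing they do not.

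**Conclusion.** The point holds for the diabetes proportional-hazards check and for the secondary time-specific or accelerated failure time estimates that depend on it. The empty first half-year for lab cases follows from the schedule alone. The distortion of period ratios is conditional: about 0.8/1.2 for a 7-day and 0.63/1.35 for a 14-day arm difference at SD 30 days, with the order reversed if the abstention arm is the later one. It would be larger with tighter visit dates and smaller with more medication-dated cases. These shifts and SDs are assumptions, because the visit windows are in the Manual of Procedures.

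The documents do not support concluding that the main diabetes comparison is biased or underpowered. The overall hazard ratio, log-rank test and planned 80% power are essentially unaffected, and the primary outcome is not involved. This is an inexpensive improvement to a secondary analysis.

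**What to change.** In section 8.1.1, for diabetes, and for prediabetes if it is analysed the same way:

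- Drop the 6-monthly option and define time-since-randomization periods by scheduled annual visit, either by visit index or with cuts midway between visits (18, 30, 42, ... months).
- State the event-date rule: lab cases go to the visit of the first abnormal draw that is later confirmed, and medication-start cases to the visit interval in which they fall.
- Keep the planned log-rank test and Cox model as the main diabetes analysis. Use a grouped-time (complementary log-log) or interval-censored model for the proportional-hazards check, the time-specific estimates and any accelerated failure time fit, allowing for the shorter final interval at close-out.

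At the same time, reconcile Table 6.1, footnote 7, which makes the annual glycaemic draw mandatory, with section 6.3.6.2, which words it as permitted. Visit-indexed periods presume that the draw is done.

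The cost is SAP wording only, with no new visits, samples or participants. The within-year dates of medication-start cases go unused in these secondary analyses, a negligible loss.

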3.5.1 TRIAL OUTCOMES

The primary, secondary, and tertiary outcomes are as follows:

Primary:

Time from baseline to a composite endpoint comprised of the first occurrence of a non-fatal myocardial infarction, non-fatal ischemic stroke, hospitalization for angina, coronary/carotid revascularization, or all-cause mortality.

Secondary:

1. Time from baseline to a composite endpoint comprised of the first occurrence of a non-fatal myocardial infarction, non-fatal ischemic stroke, hospitalization for angina, coronary/carotid revascularization, or cardiovascular death.
2. Progression among normoglycemic and pre-diabetes individuals to American Diabetes Association (ADA)-defined diabetes.¹

Tertiary:

1. Time from baseline to a composite endpoint comprised of the first occurrence of a non-fatal myocardial infarction, non-fatal ischemic stroke, or cardiovascular death.
2. Time from baseline to the first occurrence of each of the components of primary outcome (5 outcomes).
3. Time from baseline to cardiovascular death.
4. Progression among normoglycemic individuals to ADA-defined prediabetes.¹

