6.3.5 BASELINE/RANDOMIZATION

The baseline visit will be the randomization visit and will include the following assessments/procedures:

- Informed Consent – Randomization
- Anthropometrics, blood pressure, and pulse
- Concomitant medications
- Sociodemographics
- Blood draw for AST, ALT, GGT, and lipid panel (total cholesterol, HDL-C, triglycerides, and either measured or calculated LDL [if total cholesterol was drawn at screening, it does not need to be repeated]). Fasting glucose and/or HbA1c will be drawn per clinic preference. If the value is above the ADA-defined cutoff for pre-diabetes (see MOP for further detail), the participant will be asked to return to clinic for a second blood draw to confirm. (Participants with known diabetes need not have a second blood draw.)
- Collection of blood, urine and hair clippings (optional) for storage; optional genomic material will also be stored from this visit
- Smoking History
- Fagerstrom Test of Nicotine Dependence
- EQ-5D-5L™
- Confirmation of eligibility
- Behavioral assessment interview
- Randomization
- Coaching session on assigned intervention

Clinical sites may choose to do the baseline data collection and randomization over 2 visits. When the randomization is not done on the baseline visit day, the goal will be to do the randomization within 30 days. Continued eligibility will be confirmed on the day of randomization.

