8.2 SAMPLE SIZE CALCULATIONS

Sample size calculations involved extensive explorations over a range of primary endpoint definitions and baseline rates, baseline adherence rates and improvements to these due to household network effects, proportions of households with 1, 2 and 3 eligible members, intra-household correlation coefficients, and minimum expected effect sizes.

We originally assumed that our trial will be individually randomized trial, and that the primary combined expanded CVD incidence endpoint in the abstention arm will have a rate of 0.026/person-year, modestly higher than the 2.2% annual rate observed in SPRINT,¹⁵ increased slightly because, unlike SPRINT, we are including diabetic individuals and total mortality as an outcome and excluding CHF alone. Participants will enroll during the first 3 years and then will be followed for an average of 6 years. We have assumed that there will be 1% annual loss to follow-up (LTF) in both groups, and 10% non-adherence at any point in time over follow-up for participants who are the sole person in their household to be randomized, leading, for these participants, to an effective hazard ratio of 0.838 under an assumed true hazard ratio of 0.82 as in Ronksley, et al.¹⁶ Under these assumptions, to provide a minimum of 80% power at a two-sided 0.05 significance level for detecting a 18% relative decrease in the intervention group endpoint rate, for an individually randomized trial design with one participant per household, we will need 3,900 participants per arm,¹⁷ for a total of 7,800.

Although we conservatively powered the trial for an expected relative risk (RR) of 0.82, there is substantial evidence suggesting that for CVD, an RR of 0.75 is likely to be observed. If so, we will have adequate power for baseline rates as low as approximately 0.0125/person-year, significantly lower than the observed rate in MESA.

[figure not shown]
TABLE 8.1: POWER FOR CARDIOVASCULAR DISEASE ANNUAL EVENT RATES

Annual Event Rate	Relative Risk		
	RR=0.82	RR=0.80	RR=0.75
1.4%	55%	65%	84%
1.8%	65%	75%	92%
2.2%	74%	83%	96%
2.6%	80%	88%	98%
3.0%	85%	92%	99%
3.4%	89%	94%	99%

Figure 8.1 presents power for different values of relative risks (0.80, 0.82 and 0.84) as a function of a range of plausible annual events rates (from 0.014/year to 0.035/year).

FIGURE 8.1: POWER FOR PRIMARY ENDPOINT

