Power for primary endpoint (n=7,800, 1% annual LTF and 10% non-adherence in single households, 9% in multiple participant households, ICC=0.005, proportion of households with ≥ 2 members=70%, proportion of additional household members eligible=30%)

For the secondary diabetes outcome, with $\alpha=0.05$ and assuming baseline prevalence of diabetes of 25% leading to an available sample size of 5,850, with an assumed diabetes incidence rate of 0.017/person-year in the abstention arm, as consistent with an 8.2% cumulative incidence in MESA over 5 years of follow-up among 45-84 year olds,¹⁸ and with all assumptions as above concerning household clustering parameters, the table below displays the minimum power to detect RR for diabetes under even lower annual diabetes rates than has been assumed.

TABLE 8.2: MINIMUM POWER FOR DIABETES ANNUAL EVENT RATES

Minimum Power for Diabetes (n=5,850, 1% annual LTF and 10% non-adherence in single households, 9% in multiple participant households, ICC=0.005, proportion of households with ≥ 2 members=70%, proportion of additional household members eligible = 30%)			
Annual Event Rate	Relative Risk		
	RR=0.80	RR=0.75	RR=0.70
1.3%	50%	70%	85%
1.5%	55%	75%	90%
1.7%	60%	80%	93%

The trial will be adequately powered to detect relative risks of 0.75 and lower for diabetes over a plausible range of baseline event rates, assuming a baseline prevalence of 25%. The proportion of participants who have diabetes at baseline will not change the power to detect the primary outcome, but it will change the power to detect the effect of alcohol on risk of diabetes, the secondary study outcome. If the proportion of participants with diabetes at baseline is 30% rather than 25%, we will have power to detect a RR of 0.74 instead of 0.75 if the background incidence rate is 1.7%/person/year as expected, 0.73 instead of 0.74 if the background rate is 1.5%, and 0.71 instead of 0.72 if the background rate is as low as 1.3%. If the proportion of enrolled participants with prevalent diabetes exceeds expectation, potential limits to enrollment may be considered in conjunction with the DSMB to ensure adequate power for this outcome (see Section 8.5).

TABLE 8.3: MAXIMUM DETECTABLE RELATIVE RISK FOR DIABETES

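### The diabetes test accounts for clinical site only; adding baseline glycemic category would gain roughly 1 to 4 points of power under assumed inputs, at no cost in data

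*Combined protocol and SAP*

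**What the plan says.** Section 8.1.1 describes the primary analysis: a log-rank test for clustered data, "stratified by clinical site, and will be used to assess the statistical significance of any differences observed", with hazard ratios from a Cox model that carries site indicators. Diabetes is then covered in one line: "The analysis of the secondary endpoint, incidence of diabetes, will be conducted as described above". Glycemic status is neither a stratum nor a covariate in that test.

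The endpoint in Section 3.5.1 is "Progression among normoglycemic and pre-diabetes individuals to American Diabetes Association (ADA)-defined diabetes", so two groups with different starting points are pooled by definition. A tertiary outcome in the same section is restricted to normoglycemic people, so the trial has to separate the two groups in any case.

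The information is collected. Footnote 7 of Table 6.1 (Section 6.1) says that "all participants must have fasting glucose or HbA1c per clinic preference (fasting not required for HbA1c) drawn at the baseline visit and annually thereafter". For a value above the pre-diabetes cutoff, Section 6.3.5 adds that "the participant will be asked to return to clinic for a second blood draw to confirm".

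Section 8.1.1 also plans covariate-adjusted models, one for the factors most out of balance and one for all measured risk factors. Both are secondary analyses, and neither names glucose status.

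The power statement for diabetes is in Section 8.2, "assuming baseline prevalence of diabetes of 25% leading to an available sample size of 5,850". Table 8.2 gives 80% power at 1.7% per year and a relative risk of 0.75.

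**The concern.** If pre-diabetic participants progress faster than normoglycemic ones, a test that ignores the distinction loses power in two ways. High-risk people leave the risk set sooner in the arm with the higher hazard, so the pooled hazard ratio drifts toward 1 during follow-up. Chance imbalance in pre-diabetes between the arms also enters the test as noise. Stratifying on the category removes most of both.

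The secondary objective has little room. Table 8.2 reaches 80% at a relative risk of 0.75 only at the expected rate of 1.7% per year. Section 8.2 also contemplates limits on enrollment if baseline diabetes prevalence is higher than expected. Its worked case, 30% instead of 25%, removes 5,850 - 5,460 = 390 participants, or 390/5,850 = 6.7%.

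**Working it through.** **Inputs from the documents.** n = 5,850; abstention-arm rate 0.017 per person-year; relative risk 0.75; two-sided alpha 0.05; 1% annual loss; follow-up of 4.5 to 7.5 years (Section 3.1), taken as uniform; 1:1 allocation. Section 8.2 turns a hazard ratio of 0.82 into 0.838 at 10% non-adherence, which is 0.9 x HR + 0.1. For 0.75 this gives 0.9 x 0.75 + 0.1 = 0.775. An ICC of 0.005 gives a design effect of about 1.001, which is ignored.

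**Assumed.** The share of the analysis population with pre-diabetes, and the pre-diabetes to normal incidence ratio.

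**Step 1: reproduce Table 8.2.** Exponential hazards give about 491 events. Schoenfeld power is Phi(|ln HR| x sqrt(events)/2 - 1.96) = Phi(0.2549 x 22.15/2 - 1.96) = Phi(0.86) = 80.6%, against a stated 80%. At 1.7% per year, relative risks of 0.80 and 0.70 give 60.4% and 93.1% (stated 60% and 93%). All nine cells agree within 2 points, so the base is sound.

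**Step 2: split into two risk groups.** For share q and ratio R, solve for the normoglycemic hazard L in (1-q)exp(-6L) + q exp(-6LR) = exp(-6 x 0.017), which keeps overall six-year control incidence at the plan's value. For q = 0.4 and R = 5, L = 0.67% and LR = 3.37% per year. Check: 0.6 x 0.960 + 0.4 x 0.817 = 0.903 = exp(-0.102).

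**Step 3: compare the tests.** Apply a hazard ratio of 0.775 within each group. Power is Phi(|E(O-E)|/sqrt(V) - 1.96), with observed minus expected and its variance computed either on the pooled risk set or within group and summed.

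| Share, ratio | Without category | With category | Gain |
|---|---|---|---|
| 50%, 3 | 79.4% | 80.3% | 0.9 |
| 40%, 5 | 78.2% | 80.4% | 2.1 |
| 30%, 8 | 76.3% | 80.5% | 4.1 |

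(Gains are taken before rounding.) Over shares of 20-60% and ratios of 3-10 the gain runs from 0.7 to 6.5 points. At a ratio of 2 it is about 0.3 to 0.4.

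**Step 4: simulation.** With 6,000 trials per scenario, 16 sites and annual detection, site strata are compared with site-by-category strata. Power goes from 80.0% to 81.3% (50%, 3), 78.0% to 79.8% (40%, 5) and 75.4% to 79.7% (30%, 8). When category is not prognostic, nothing is lost beyond simulation error (79.5% against 79.4%).

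**Step 5: imperfect classification.** If the ratio applies to confirmed status and one draw has sensitivity 0.8 and specificity 0.9 (both assumed), the three gains become 0.5, 1.1 and 2.0 points.

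**Step 6: read 0.75 as the pooled effect.** Set the within-group hazard ratio so that the test without category keeps its 80.6%. With category, power is then 81.5% to 84.4% for shares of 30-50% and ratios of 3-8, a gain of 0.9 to 3.8 points.

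**The case against.** **No error is shown.** The test matches the randomization stratum in Section 8.4, its type I error is correct, and Table 8.2 reproduces. This stands: the point is about efficiency alone.

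**The size rests on figures the documents do not contain.** This also stands. Neither the share nor the ratio is given, and at a ratio of 2 the gain is negligible. The direction depends only on glycemic category being prognostic, and if it is not, stratifying costs nothing.

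**A reader might infer that true power is below the stated 80% and that the tables hide a loss.** The documents do not support that. It requires 0.75 to be the effect within each glycemic group, whereas Section 8.2 states it for the non-diabetic population as a whole, without a split. Read as the pooled effect, site-only power stays at the plan's figure and stratification raises it above 80%. Likewise, the pooled hazard ratio lying nearer to 1 is a difference between a marginal and a conditional effect measure. It is not bias.

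**Classification before randomization is imperfect.** Section 3.5.2 defines ADA status by two measurements, and under Section 6.3.5 the confirming draw can follow randomization. A single value, glucose or HbA1c by clinic preference, will misclassify some people. This stands, and Step 5 shows that it can halve the gain. Stratifying within site largely absorbs the choice of assay.

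**The adjusted analyses already cover it.** Only in part. They help with estimation under imbalance, but they are not the test of the secondary objective.

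**Too many strata.** About 491 events over 16 to 20 sites and two categories is 491/40 = 12 to 491/32 = 15 per stratum, and the 16-site simulation shows no penalty.

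**Conclusion.** A free improvement, not a defect. The site-only diabetes test is valid but leaves efficiency unused. At n = 5,850, 1.7% per year and an effective hazard ratio of 0.775, the gain is about 1 to 4 points of power, conditional on an assumed pre-diabetes share of 30-50%, an assumed incidence ratio of 3-8 and accurate classification. It is under 1 point at a ratio of 2 and about half as large under the misclassification assumed above. The direction is secure if category is prognostic; the size is not, and should always be quoted with its assumptions.

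**What to change.** In Section 8.1.1, before any unblinded outcome data are seen, replace the cross-reference for diabetes with a statement of these points:

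- The diabetes log-rank test and Cox model, both still for clustered data, are stratified by clinical site and by baseline glycemic category (normal or pre-diabetes).
- Category is taken from the sample drawn before randomization, without waiting for the confirmatory draw. If a site draws both glucose and HbA1c, name which one counts.
- The reported hazard ratio is conditional on glycemic category.
- Adjustment for continuous baseline glucose or HbA1c is a sensitivity analysis.

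The cost is a few lines of text. No new data, visits or participants are needed. The timing matters because a stratum chosen after outcomes are known could be challenged as data-driven.
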